### **10.1.5 Follow-up**

Patients still taking the IMP at the time of the Study Closeout Visit (ie, who have not prematurely permanently discontinued IMP) will have their final study visit (Follow-up Visit) 14 days ( $\pm 4$  days) after their Study Closeout Visit.

#### **10.1.5.1 Follow-Up Visit**

Patients who have attended a pEOT Visit do not need to attend this Visit. The following procedures/assessments will be performed at this Visit:

- Vital signs (sitting BP, heart rate)
- Abbreviated physical examination, including lower extremities
- Measurement of eGFR
- IRT contact
- AEs, including SAEs/AESIs/EOSIs (including severe hypoglycemia) and endpoint events (if any) are collected (if a renal endpoint relating to a reduction in eGFR is suspected, see [Section 9.1.2.1](#))

## 10.2 DEFINITION OF SOURCE DATA

Evaluations recorded in the e-CRF must be supported by appropriately signed source documentation related but not limited to the following:

- Agreement and signature of ICF with the study identification
- Study identification (name)
- Patient number, confirmation of randomization, treatment batch number, dates and doses of study treatment administration
- Medical, surgical, diabetes history, including information on:
  - Demography, inclusion and exclusion criteria
  - Last participation in a clinical trial
  - Contraception method for WOCBP
  - Previous and concomitant medication
- Dates and times of visits and assessments including examination results
- Vital signs, height, body weight, laboratory reports, investigation results (eg, ECG traces, imaging reports)
- Adverse events and follow-up:
  - In case of AESI/SAE, the site should file in the source documents at least copies of the hospitalization reports and any relevant examination reports documenting the follow-up of the SAE
  - In case of endpoint events, the site should file in the source documents at least copies of the hospitalization reports and any relevant examination reports documenting the follow-up of the event
- Date of premature treatment discontinuation (if any) and reason
- Date of premature study discontinuation (if any) and reason
- Nursing notes
- Dietician's notes
- Physician's notes

## 10.3 HANDLING OF PATIENT TEMPORARY OR PERMANENT TREATMENT DISCONTINUATION AND OF PATIENT STUDY DISCONTINUATION

The IMP should be continued until the Study Closeout Visit whenever possible. In case the IMP is stopped, it should be determined whether the stop can be made temporarily; permanent IMP discontinuation should be a last resort. Any IMP discontinuation must be fully documented in the e-CRF. In any case, the patient should remain in the study and be followed for the remainder of the study duration to collect vital safety status and endpoint data. Where the patient is taking

2 tablets of IMP qd (corresponding to sotagliflozin 400 mg or matching placebo), consideration should be given to reducing the dose to 1 tablet of IMP qd (corresponding to sotagliflozin 200 mg) prior to temporary treatment discontinuation (see [Section 8.1.1.2](#)). In this case, the 200 mg dose will be maintained for the duration of the remaining double-blind study treatment period.

### **10.3.1 Temporary treatment discontinuation with investigational medicinal products**

All IMP discontinuation should initially be considered as temporary unless permanent discontinuation is mandated by the protocol (see [Section 10.3.3](#)), and the Investigator should make best effort to resume IMP treatment as early as practically possible. There is no defined limit to the duration of temporary discontinuation. This is in part due to the fact that a patient is expected to participate in the study for a period potentially lasting several years. Reinitiation of treatment with the IMP will be done under close and appropriate clinical and/or laboratory monitoring once the Investigator is satisfied that, according to his/her best medical judgment, the IMP was unlikely to be responsible for the event concerned.

Temporary treatment discontinuation may be considered by the Investigator because of suspected AEs. Lower extremity complications (such as skin ulcers, infection, osteomyelitis, and gangrene) requiring treatment should lead to temporary discontinuation of IMP.

If DKA is suspected or confirmed, study treatment should be stopped immediately and should not be re-started unless another cause for the ketoacidosis is identified and resolved.

In addition, IMP administration should be stopped in patients admitted to the hospital for major surgical procedures or due to serious illness.

If a patient who is on an ACE-i/ARB does not tolerate the combination of the ACE-i/ARB with IMP due to hypotension/volume depletion, and one of the two agents (either the ACE-i/ARB or IMP) needs to be withheld, the ACE-i/ARB should be maintained, and the IMP should be withheld (temporarily if possible).

Reinitiation of treatment with the IMP will be done under close and appropriate clinical/and or laboratory monitoring once the Investigator is satisfied that, according to his/her best medical judgment, the responsibility of the IMP in the occurrence of the concerned event was unlikely.

Temporary discontinuation of IMP due to intolerance should be followed by reinitiation of 1 tablet of IMP qd (sotagliflozin 200 mg/matching placebo). Temporary discontinuation for any other reason should be followed by reinitiation of IMP at the last dose tolerated prior to discontinuation where possible.

For all confirmed temporary treatment discontinuations, the start date and end date of the period with no IMP treatment should be recorded by the Investigator in the appropriate pages of the e-CRF. Additionally, temporary discontinuation should be recorded in the IRT.

Patients who temporarily discontinue IMP should be reassessed at every visit to determine whether it is possible to safely resume IMP. If a decision has been made that the discontinuation is

permanent, then the patient should be considered as permanently discontinued and the corresponding e-CRF page should be completed. Please note that permanent discontinuation should be a last resort.

### **10.3.2 Permanent treatment discontinuation with investigational medicinal product(s)**

Permanent treatment discontinuation is any treatment discontinuation associated with the definitive decision from the Investigator not to re-expose the patient to the IMP at any time during the study, or from the patient not to be re-exposed to the IMP whatever the reason.

If a patient refuses to continue in the study after premature IMP discontinuation, and the pEOT Visit is <10 days after the last IMP administration, then every effort should be made to secure a follow-up contact is performed  $\geq 14$  days ( $\pm 4$  days) after the last IMP intake with procedures normally performed at the Follow-up Visit (see [Section 10.1.5.1](#)). If the patient does not agree to on-site visits, he/she will be contacted by telephone to inquire about safety status (including hospitalizations and endpoints). Every effort should be made to collect endpoint information and vital status at least once a year and at the time of Study Closeout.

If after permanent treatment discontinuation, a patient who has withdrawn consent for treatment has reconsidered the decision to permanently discontinue treatment and wishes to later resume IMP, and if the Investigator has determined there is no safety reason prohibiting the patient from resuming IMP and the selection criteria for the study are still met, the patient may resume IMP with Sponsor approval.

### **10.3.3 List of criteria for permanent treatment discontinuation**

The patients may withdraw from treatment with the IMP if they decide to do so, at any time and irrespective of the reason, or this may be the Investigator's decision. All efforts should be made to document the reason(s) for treatment discontinuation and this should be documented in the e-CRF.

Patients who report a CV or renal endpoint as described in [Section 10.4.1.4](#) should remain on IMP until the end of the study, unless there is a safety concern.

The following reasons shall lead to permanent IMP discontinuation:

- At the patient's own request (ie, withdrawal of consent for treatment) (note that this is regardless of whether or not the patient continues in the study)
- If, in the Investigator's opinion, continuation with the administration of the study treatment would be detrimental to the patient's well-being
- Pregnancy (in female patients)
- Any code breaking requested by the Investigator
- Specific request of the Sponsor
- Patient requires dialysis or renal transplantation

- Estimated glomerular filtration  $<15 \text{ mL/min/1.73 m}^2$

**Note:** the central laboratory will alert the Investigator for eGFR values  $<15 \text{ mL/min/1.73 m}^2$ . A repeat determination should be performed within 2 weeks, and study treatment discontinued if the repeat eGFR is  $<15 \text{ mL/min/1.73 m}^2$  (unless a reversible cause is identified [eg, short-term illness or transient volume depletion], in which case an additional repeat determination can be performed after resolution of the short-term illness).

Any abnormal laboratory value or ECG parameter will be immediately rechecked for confirmation before making a decision of permanent discontinuation of the IMP for the concerned patient.

#### **10.3.4 Handling of patients after permanent treatment discontinuation**

Every effort should be made to maintain patients in the study. All patients will be followed until the last visit according to the study procedures specified in this protocol, or up to recovery or stabilization of any AE to be followed-up as specified in this protocol, whichever comes last. The scientific value of the complete collection of data will be explained to patients, and site personnel will receive training regarding strategies for patient retention, and access to tools to assist with this during the study.

For patients who prematurely permanently discontinue the IMP, a pEOT Visit (see [Section 10.1.3](#)) will be scheduled as soon as possible after time of discontinuation (the latest at the next on-site visit). The reason for the IMP discontinuation shall be clearly specified.

For patients who discontinue IMP but remain in the study, the remaining visits should occur as scheduled where possible. All efforts should be made to continue to follow the patients for primary and secondary endpoints, after the discontinuation of treatment.

All cases of permanent treatment discontinuation must be recorded by the Investigator in the appropriate pages of the e-CRF when considered as confirmed.

#### **10.3.5 Procedure and consequence for patient withdrawal from study**

The patients may withdraw from the study before study completion if they decide to do so, at any time and irrespective of the reason without any effect on their care. However, if patients no longer wish to take the IMP, they will be encouraged to remain in the study.

The Investigators should discuss with them key visits to attend. The value of all their study data collected during their continued involvement will be emphasized as important to the public health value of the study.

Patients who withdraw from the study treatment should be explicitly asked about the contribution of possible AEs to their decision, and any AE information elicited must be documented.

All study withdrawals must be recorded by the Investigator in the appropriate screens of the e-CRF and in the patient's medical records. In the medical record, at least the date of the withdrawal and the reason should be documented.

In addition, a patient may withdraw his/her consent to stop participating in the study. Withdrawal of consent for patient contacts should be distinguished from withdrawal of consent for non-patient contact follow-up, medical records check. The site should document any case of withdrawal of consent.

For patients who fail to return to the site, unless the patient withdraws consent for contact, the Investigator must make the best effort to recontact the patient, and to determine his/her health status, including at least his/her vital status (including time of death). Attempts to contact such patients (3 phone call attempts followed by a certified letter) must be documented in the patient's records (eg, times and dates of attempted telephone contact, receipt for sending a registered letter). If a patient withdraws consent for follow-up, the Investigator should still make best efforts to determine the patient's health status, including at least his/her vital status (including time of death), where permitted by local regulations. The patient's final vital status will be confirmed at the time of the Study Closeout Visit.

Patients who have withdrawn from the study cannot be rerandomized in the study. Their inclusion and treatment numbers must not be reused.

## **10.4 OBLIGATION OF THE INVESTIGATOR REGARDING SAFETY REPORTING**

### **10.4.1 Definitions of adverse events**

#### **10.4.1.1 Adverse event**

An **adverse event** (AE) is any untoward medical occurrence in a patient or clinical investigation patient administered a pharmaceutical product and which does not necessarily have to have a causal relationship with this treatment. Cardiovascular endpoints, and their components, specified in this study (as per [Section 10.4.2](#)) will not generally be considered as AEs, and will be waived from expedited reporting to Health Authorities, Investigators, independent ethics committee (IECs)/institutional review boards (IRBs), etc. For further details please refer to [Section 10.4.2](#).

#### **10.4.1.2 Serious adverse event**

A **serious adverse event** (SAE) is any untoward medical occurrence (with the exception of those events waived as efficacy endpoints, see [Section 10.4.1.4](#)) that at any dose:

- Results in death, or
- Is life-threatening, or  
**Note:** The term "life-threatening" in the definition of "serious" refers to an event in which the patient was at risk of death at the time of the event; it does not refer to an event which hypothetically might have caused death if it were more severe.
- Requires inpatient hospitalization or prolongation of existing hospitalization, or

- Results in persistent or significant disability/incapacity, or
  - Is a congenital anomaly/birth defect
  - Is a medically important event
- Medical and scientific judgment should be exercised in deciding whether expedited reporting is appropriate in other situations, such as important medical events that may not be immediately life-threatening or result in death or hospitalization but may jeopardize the patient or may require medical or surgical intervention (ie, specific measures or corrective treatment) to prevent 1 of the other outcomes listed in the definition above.

**Note:** The following list of medically important events is intended to serve as a guideline for determining which condition has to be considered a medically important event. The list is not intended to be exhaustive:

- Intensive treatment in an ED or at home for:
  - Allergic bronchospasm
  - Blood dyscrasias (ie, agranulocytosis, aplastic anemia, bone marrow aplasia, myelodysplasia, pancytopenia, etc),
  - Convulsions (seizures, epilepsy, epileptic fit, absence, etc).
- Development of drug dependence or drug abuse
- ALT >3 x ULN + total bilirubin >2 x ULN or asymptomatic ALT increase >10 x ULN (Please refer to related flowchart in [Appendix E](#))
- Suicide attempt or any event suggestive of suicidality
- Syncope, loss of consciousness (except if documented as a consequence of blood sampling)
- Bullous cutaneous eruptions
- Cancers diagnosed during the study or aggravated during the study
- Chronic neurodegenerative diseases (newly diagnosed) or aggravated during the study
- Venous thrombotic events to include deep venous thrombosis and thromboembolism (to include pulmonary embolism)
- Pancreatitis
- Bone fractures
- Adverse events leading to amputation(s)
- Diabetic ketoacidosis

#### **10.4.1.3 Adverse event of special interest**

An **adverse event of special interest** (AESI) is an AE (serious or nonserious) of scientific and medical concern specific to the Sponsor's product or program, for which ongoing monitoring and immediate notification by the Investigator to the Sponsor is required. Such events may require

further investigation in order to characterize and understand them. Adverse events of special interest may be added, modified or removed during a study by protocol amendment.

The AESIs for this study are:

- Pregnancy of a female patient entered in a study as well as pregnancy occurring in a female partner of a male patient entered in a study with IMP: It will be qualified as an SAE only if it fulfills 1 of the seriousness criteria (see [Section 10.4.1.2](#)).
  - In the event of pregnancy in a female participant, IMP should be discontinued.
  - Follow-up of the pregnancy in a female participant or in a female partner of a male participant is mandatory until the outcome has been determined (see [Appendix A](#)).
- Symptomatic overdose (serious or nonserious) with IMP
  - An overdose (accidental or intentional) with the IMP is an event suspected by the Investigator or spontaneously notified by the patient (not based on systematic pills count) and defined as administration of more than twice the intended daily dose of IMP within a 24-hour period..
  - Of note, asymptomatic overdose has to be reported as a standard AE.
- ALT  $\geq 3$  ULN (if baseline ALT < ULN) or ALT  $\geq 2$  times the baseline value (if baseline ALT  $\geq$  ULN) (Please refer to related flowchart in [Appendix D](#)).

#### **10.4.1.4 Events of special interest**

An **event of special interest** (EOSI) is a serious or non-serious AE of scientific and medical concern specific to the Sponsor's product or program, for which ongoing monitoring may be appropriate. Such events may require further investigation in order to characterize and understand them. These events should be reported in e-CRF (where applicable) and will only qualify for expedited reporting when serious (fulfilling SAE criteria). Please refer to the study e-CRF completion guidelines for additional details on e-CRF completion.

A dedicated safety analysis will be performed as described in [Section 11.4.3.4](#) and in the SAP to evaluate whether there is an imbalance in any of the below events with sotagliflozin relative to placebo.

The EOSIs for this study are:

- Venous thrombotic events to include deep venous thrombosis and thromboembolism (to include pulmonary embolism)
- Pancreatitis
- Bone fractures
- Adverse events leading to amputation(s)
- Diabetic ketoacidosis (see [Section 10.4.7](#) for further details)

- Malignancies of special interest (breast, bladder, renal cell, Leydig cell, pancreatic, prostate, and thyroid follicular cell carcinoma)
- Genital mycotic infections (to include vulvovaginal candidiasis in females and candidal balanitis in males)
- Urinary tract infections
- Diarrhea
- Clinically relevant volume depletion and events related/possibly related to volume depletion
- Severe hypoglycemia (see [Section 10.6.1](#))

#### **10.4.2 Serious adverse events waived from expedited regulatory reporting to regulatory authorities**

Unlike most studies where the primary efficacy variable is the resolution or improvement of an existing condition, in this study efficacy endpoints include the occurrence of life-threatening events. Indeed, participants to this study are recruited precisely because they are at high risk for these life-threatening events. They are therefore expected to have at least 1 primary and secondary CV or renal efficacy endpoint during the course of the study.

All Cardiovascular events will be reported (within 1 working day) in the e-CRF. Detailed process for the exchanges with the CEC will be described in a specific Manual of Operations.

In light of the above, suspected all CV events as specified in this protocol will not be considered as AEs, will not be reported to pharmacovigilance, and are waived from regulatory reporting to Health Authorities except if the Investigator, according to his/her best medical judgment, considers these events as related to the IMP taking into consideration the patient's underlying disease. In that case, the Investigator will report it within 24 hours to the Sponsor.

Expedited reporting for the following all CV events will be waived:

- Cardiovascular death
- Any MI
- Unstable angina
- Any stroke
- Heart failure leading to hospitalization
- Urgent HF visit (as defined in [Appendix B](#))

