### **9.1.3 Other efficacy endpoints**

All the following endpoints are assessed in the total patient population:

- Proportion of patients with HHF or urgent HF visit (see [Appendix B](#)) within 30 days of Randomization
- Changes in KCCQ-12 scores from Baseline to Week 2, Month 1, Month 4, Month 8, Month 12, then annually
- Time to  $\geq 50\%$  decrease in eGFR from Baseline
- Proportion of patients with  $\geq 1$  new onset of atrial fibrillation, atrial flutter, or ventricular arrhythmia from Randomization
- Time to first MI (fatal and nonfatal)
- Time to first stroke (fatal and nonfatal)
- Changes from Baseline to Month 1 and Month 4 for NT-proBNP
- Changes from baseline in loop diuretics at day 180 and/or end of treatment visit
- Changes in hemoconcentration from Baseline at Week 2, Month 1, Month 4, Month 12, and EOT
- Changes from Baseline to Month 4, Month 12, and Month 24 in:
  - Hemoglobin A1c
  - Body weight

- Time to first occurrence of either of the following clinical events in subgroups of patients who started first IMP dose prior vs. after hospital discharge (or urgent care facility where appropriate):
  - Cardiovascular death
  - Hospitalization for heart failure

The following endpoints are assessed in subgroups of patients defined by LVEF:

- Time to first occurrence of either of the following clinical events in patients with LVEF <40%:
  - Cardiovascular death
  - Hospitalization for heart failure
- Time to first occurrence of either of the following clinical events in patients with LVEF  $\geq$ 40% to <50%:
  - Cardiovascular death
  - Hospitalization for heart failure
- Time to first occurrence of either of the following clinical events in patients with LVEF  $\geq$ 50%:
  - Cardiovascular death
  - Hospitalization for heart failure
- Time to all-cause mortality in patients with LVEF <40%
- Changes in hemoconcentration from Baseline at Week 2, Month 1, Month 4, Month 12, and EOT in patients with LVEF <40%

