### ***2.1.3.3 Other efficacy endpoints***

- First occurrence of CV death, HHF, or urgent visit for HF
- First occurrence of CV death or HHF
- Total occurrences (first and potentially subsequent) of HHF after randomization
- Total occurrences (first and potentially subsequent) of urgent HF visits after randomization
- First occurrence of CV death, HHF, urgent visit for HF, non-fatal myocardial infarction, and non-fatal stroke
- First occurrence of fatal and non-fatal MI
- First occurrence of fatal and non-fatal stroke
- First occurrence of new onset of atrial fibrillation or atrial flutter (adverse events (AEs) with a preferred terms (PTs) of atrial fibrillation or atrial flutter)
- First occurrence of a composite renal endpoint, consisting of events sustained  $\geq 50\%$  decrease in eGFR from baseline (for  $\geq 30$  days), chronic dialysis, renal transplant, or sustained eGFR  $< 15$  mL/min/1.73m^2 (for  $\geq 30$  days)
- First occurrence of severe hypoglycemia
- Total occurrences of the following hypoglycemia categories
  - Severe hypoglycemia
  - Hypoglycemia with documented glucose value  $< 54$  mg/dL
  - Hypoglycemia with documented glucose value  $< 70$  mg/dL
- Days alive and out of hospital (DAOH) and percent DAOH (PDAOH)

- Changes from baseline in NT-proBNP, hematocrit, HbA1c, body weight, and SBP

All time-to-event endpoints are assessed based on investigator-reported events.

Cardiovascular death includes death of undetermined cause.

The first occurrence of the composite renal endpoint is defined as follows:

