#### ***a. General censoring rule for primary efficacy endpoint:***

For patients who have no primary CV endpoints, they will be censored using the following rules:

- Patients who completed the study will be censored at their last study visit date (study close-out visit date or final follow-up visit date, whichever later).  
Note: If there are CV events happening after the patient's last study visit and the event's proceeding/related event's onset date is on or before the patient's last study visit date, in this case, this CV events will be included in efficacy analysis.

Another example, for a HHF, if the onset date of HF is before last study visit and its resulted hospitalization is after last study visit, this HHF will be included in efficacy analysis.

- Patients who died without discontinuing the study before death (ie Death reported on the 'Completion of End of Study') will be censored at their date of Non-CV death
- Patients who discontinued the study will be censored at their later of study discontinuation date or latest date with cardiovascular efficacy endpoint information (MI/UA, heart failure, cerebrovascular event, or coronary procedure, admission to hospital/emergency room, cardiac biomarkers) collected

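### Unstable angina can be read as exempt from adverse event status as a CV endpoint event, yet it is in no endpoint, so no planned table identifies by arm the non-fatal cases judged unrelated to study drug

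*Protocol*

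**What the plan says.** Protocol Section 10.4.2 reasons that, because the efficacy endpoints include life-threatening events, CV events need separate handling. It states that "suspected all CV events as specified in this protocol will not be considered as AEs, will not be reported to pharmacovigilance". There is one exception: the investigator still reports to the Sponsor if he or she "considers these events as related to the IMP taking into consideration the patient's underlying disease". A separate sentence then introduces a list of events for which expedited reporting is waived. One of its six entries is "Unstable angina".

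Section 10.4.1.1, which defines an AE, refers to Section 10.4.2 for the study's CV endpoints and their components. It says that these "will not generally be considered as AEs, and will be waived from expedited reporting to Health Authorities".

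The data are still to be captured: "All Cardiovascular events will be reported (within 1 working day) in the e-CRF".

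In both documents the coronary endpoints are limited to myocardial infarction (MI). SAP Section 2.1.3.3 lists "First occurrence of fatal and non-fatal MI". The SAP refers to unstable angina once, in the censoring rule for the primary endpoint in Appendix A. There it counts as CV endpoint information that can set a censoring date: "MI/UA, heart failure, cerebrovascular event, or coronary procedure".

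**The concern.** Taking an event out of the AE tables because it is an endpoint is sound only if the efficacy tables then report it. For unstable angina that second half appears to be missing. A potentially serious ischaemic event, in a high-risk heart failure population, could be collected and yet have no output that names it by treatment arm. If sites also differ in whether they enter it as an AE, the AE tables would hold an unknown share of the cases while looking complete.

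**Working it through.** There is no figure to recompute. The check sets the waived list against every place where an event could be tabulated.

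**Step 1. Waived events against endpoints.**

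| Event waived in Protocol 10.4.2 | Protocol endpoint | SAP endpoint |
|---|---|---|
| CV death | 9.1.1 (primary) | 2.1.3.1 (primary) |
| MI | 9.1.3 (other) | 2.1.3.2 (non-fatal, in a composite); 2.1.3.3 |
| Unstable angina | none | none |
| Stroke | 9.1.3 (other) | 2.1.3.2 (non-fatal, in a composite); 2.1.3.3 |
| Heart failure hospitalisation | 9.1.1 (primary) | 2.1.3.1 (primary) |
| Urgent heart failure visit | 9.1.2 (secondary) | 2.1.3.1 (primary) |

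Five of six map to an analysed endpoint or component. One does not.

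**Step 2. Special-interest lists.** Unstable angina is not an adverse event of special interest (Protocol 10.4.1.3; SAP 2.1.4.1). It is not an event of special interest either (Protocol 10.4.1.4; SAP 2.1.4.1).

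**Step 3. General safety tables.** SAP 2.4.5.1 tabulates treatment-emergent AEs and serious AEs by system organ class and preferred term. An event that the site did not record as an AE does not enter them.

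**Step 4. Where each kind of case ends up if the exemption applies.**

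- Judged related to study drug: outside the exemption (Protocol 10.4.2).
- Fatal: counted in CV death and all-cause mortality (SAP 2.1.3.2).
- Non-fatal, unrelated, hospitalised: counted in days in hospital and in the reasons-for-hospitalisation summary (SAP 2.4.4.4). The example categories there are heart failure, other efficacy event and non-efficacy AE. Unstable angina is not named and, under the exemption, fits none of these cleanly.
- Non-fatal, unrelated, not hospitalised: no planned table.

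So for non-fatal, unrelated cases no output identifies the event by arm, whether or not the patient was hospitalised.

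**Step 5. How firm the exemption is.** The sentence removing AE status covers CV events specified in the protocol. The sentence that leads into the list waives only expedited reporting. Section 10.4.1.1 ties the non-AE rule to Section 10.4.2, but qualifies it as a general rule. Sections 10.4.1.2 and 11.4.3.1 send the reader to Section 10.4.1.4 for the waived efficacy events, and that section is the special-interest list. A site could reasonably reach either answer.

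**The case against.** The strongest reply is that the exemption is an inference. Unstable angina is listed only beneath the sentence waiving expedited reporting, and the section heading itself calls the listed items serious AEs. Since unstable angina is not an efficacy event, it could be argued that it stays an ordinary AE and enters the usual tables. The SAP takes precedence over the protocol where they differ (SAP 1.1). It tabulates all treatment-emergent AEs and names no excluded terms. What sites actually do depends on the e-CRF completion guidelines and the endpoint committee's manual, which are not among the documents.

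Much of this stands, and it is why the point is put as a possible reading. It does not remove the point. Section 10.4.1.1 describes the events handled in Section 10.4.2 as CV endpoints and their components, which supports the exempting reading. The SAP can tabulate only what sites record as AEs. Two defensible readings are themselves a reason to settle the matter.

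A reader might go further and infer that unstable angina appears in no table at all. The documents do not support that: related cases are excepted, fatal cases count as deaths, and hospitalised cases enter the hospitalisation analyses. Protocol Section 10.5 also commits the Sponsor to reporting all safety observations in the study report, although it specifies no table.

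It is also fair that the consequence is limited. SAP 2.4.5 plans no hypothesis testing of safety data, and MI is already analysed by arm.

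**Conclusion.** The point holds as a minor reporting gap. Unstable angina can be read as exempt from AE status on an endpoint rationale that does not apply to it. Under that reading, no planned output identifies by arm the non-fatal cases judged unrelated to study drug. Under the other reading the cases are in the AE tables. If sites split between the two, those tables are incomplete to an unknown degree.

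The documents give no expected number of unstable angina events, so the count affected cannot be estimated. No efficacy result, test or error rate changes.

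The conclusion assumes that the e-CRF guidelines and the committee manual do not already settle how sites record the event. It also rests on Amended Protocol 01. The SAP mentions an Amendment 2 whose text is not among the documents.

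**What to change.** In SAP Section 2.4.5.1, state that unstable angina counts as an AE for tabulation and that only expedited reporting is waived. Add one descriptive row or table giving the number and percentage of patients with unstable angina by arm, on-study and on-treatment. Take cases from both the CV event pages and the AE pages of the e-CRF and count each patient once, so that differences in site recording do not undercount or duplicate.

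A table of all six waived event types is not needed, because the other five are already analysed as endpoints or components.

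The cost is one small descriptive output, with no new data collection and no effect on alpha. It depends on unstable angina being recorded separately from MI. The only sign in the SAP is the joint MI/UA label in the censoring rule, so the e-CRF should be checked first.
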